2.2 Supporting Data

Our multi-institutional and multi-disciplinary research group recently completed an NIH/NIAMS funded(UM1 AR063381) randomized placebo-controlled clinical trial (N=301), FAST: Fibromyalgia Activity Study with TENS (NCT01888640), that showed Active-TENS (compared

to Placebo-TENS or No-TENS) reduced pain and fatigue during movement and at rest acutely (during the first application) and following 4 weeks of daily use. After the randomized phase, all groups received Active-TENS – there was sustained improvement in the Active-TENS group and equivalent improvement in the groups originally randomized to Placebo-TENS or No-TENS. Dramatic improvement in the global rating of change occurred for the Active-TENS group when compared to Placebo-TENS or No-TENS groups. TENS was well tolerated with <5% of participants reporting pain with TENS or irritation with the electrodes, which were the most common adverse events.

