6 CLINICAL EVALUATIONS/STUDY PROCEDURES

6.1 Schedule of Activities

Evaluation	First and Second PT Intake Visit*	Research Homework before PT Visit 3 (Day 1 ¹)	Treatment Visits	30 +/- 5 days Home ¹	60 - 5/+10 days Home ¹	65 - 5/+15 days Home (No TENS Group Only) ⁴	90 +/- 5 days Home ¹	180 +/- 5 days Home ¹
Eligibility Screen- REDCap™	X							
PSFS		X		X	X		X	X
Informed Consent/ eConsent Review	X*							
Resting NRS pain/fatigue ²		X		X	X	X	X	X
Sit and Stand Test with NRS pain and fatigue pre-treatment ³		X		X	X	X	X	X
TENS applied (or not) x 30 minutes		X	X	X	X	X	X ³	X ³
Demographics		X						
2016 FM Criteria		X						
FIQR		X		X	X		X	X
MAF		X			X			X
BPI		X		X	X		X	X
PROMIS-Physical Function		X		X	X		X	X
PROMIS-Sleep		X		X	X		X	X
PCS		X		X	X		X	X
PHQ-8		X		X	X		X	X
GAD-7		X		X	X		X	X
RAPA		X			X			X
PGIC				X	X		X	X
TAPS1		X			X			X

Concomitant Medications		X						X
Sit and Stand Test with NRS pain and fatigue post TENS or no TENS treatment after 30 min of answering questionnaires		X		X	X	X	X ³	X ³
Adverse Events				X	X		X	X
Barriers to TENS								X

* *Informational activities (e.g., video explaining study, description of TENS) will be delivered at home between PT visits. Consent will be obtained electronically before or as the initial activity of the second PT visit. After the second PT visit, participants will complete Research Homework. Day 1 is designated as the day the baseline study data is collected at home. Baseline data collection should be completed within 10 days of the second PT visit.*

¹*Assessment completed on computer or tablet, phone, or paper at home. If the participant does not have access to a computer, the data will be collected over the phone by the study team and directly entered into the database, or on paper/mailed or Faxed.*

²*Resting NSR pain/fatigue and Sit and Stand Test completed pre and post TENS treatment.*

³*All participants apply TENS*

⁴*Day 65 visit is only performed by the No Tens group*

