6.2.1 First and Second PT Intake Visit

First Visit

- PT identifies possible participant
- Complete eligibility screen on REDCap™, if interested
- If eligible, PT instructs participant to complete electronic consent before PT Clinic Visit 2.
- Provide study information, refer to study website and provide contact for study team.
- When consent is complete REDCap™ sends email to PT and study team.

Second Visit

- PT verifies eConsent completion by email or REDCap™. If consent is not complete, participant may decline or may complete eConsent in clinic before study procedures begin.
- PT provides instructions on:
 - Logging into REDCap™ and accessing forms
 - The importance of the Sit and Stand test and Research Homework
 - TENS use (if applicable)
- Complete PT treatment with physical therapist.
- PT provides TENS units, electrodes, and written brochures to TENS group.
- PT logs TENS unit serial numbers.
- Redcap link emailed to participant to complete Research Homework before PT Clinic Visit 3.

6.2.2 Day 1 Research Homework Before PT Visit 3

- Log into REDCap™ (if participant does not have access to the internet, data collection may be completed on paper and mailed or faxed to study team, or completed by phone with a study team member)
- Pre-treatment resting NRS for pain and fatigue
- Pre-treatment Sit and Stand Test with NRS for pain and fatigue.
- TENS applied (or not) for at least 30 min while completing the assessments below on tablet (no TENS participants go directly to completing the assessments)
- Complete the following assessments on REDCap™:
 - Demographics
 - 2016 FM Criteria
 - PSFS
 - FIQR
 - MAF

- BPI
- PROMIS-Physical function
- PROMIS-Sleep + Sleep duration
- PCS
- PHQ-8
- GAD-7
- RAPA
- TAPS1
- Medications
- Post-treatment resting NRS for pain and fatigue
- Post-treatment Sit and Stand Test with NRS for pain and fatigue
- REDCap™ sends email to PT and study team when Research Homework is complete

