6.2.3 PT Treatment Visits (In-clinic)

- Apply TENS during exercise treatment (TENS sites and NO TENS sites after day 65 if have in-clinic visit)

6.2.4 30 Day Research Homework (Home +/- 5 days)

- REDCap™ sends participant reminder email to complete Day 30 Research Homework
- Log into REDCap™ (or alternative method) to complete the following assessments
 - Adverse Events
 - Pre-treatment resting NRS for pain and fatigue
 - Pre-treatment Sit and Stand with NRS for pain and fatigue
- Apply TENS (or not)
 - PSFS
 - FIQR
 - BPI
 - PROMIS Physical Function
 - PROMIS-Sleep + Sleep duration
 - PCS
 - PHQ-8
 - GAD-7
 - PGIC
- Post-treatment resting NRS for pain and fatigue
- Post-treatment Sit and Stand test NRS for pain and fatigue
- REDCap™ sends email to study staff that Day 30 Research Homework is complete.

6.2.5 60 Day Research Homework (Home - 5/+10 days)

- REDCap™ sends participant reminder email to complete Day 60 Research Homework
- Log into REDCap™ to complete assessments:
 - Adverse Events
 - Pre-treatment resting NRS for pain and fatigue
 - Pre-treatment Sit and Stand Test with NRS for pain and fatigue
- Apply TENS (or not)
 - PSFS
 - FIQR
 - MAF
 - BPI

- PROMIS Physical Function
- PROMIS-Sleep + Sleep duration
- PCS
- PHQ-8
- GAD-7
- PGIC
- RAPA
- TAPS1
- Post-treatment resting NRS for pain and fatigue
- Post-treatment Sit and Stand Test with NRS for pain and fatigue
- REDCap™ sends email to study staff that Day 60 Research Homework is complete.

6.2.5.1 No TENS Group 65 Day Telehealth Visit by Study Team (Home -5/+15 days)

- Participants in no TENS clinics will be sent a TENS unit and electrodes with written instructions and links to video instructions for use through end of study.
- Study Team provides Telehealth instruction for TENS use, TENS app, and baseline Research Homework with TENS
- Participant completes Baseline Research Homework:
 - Log into REDCap™
 - Pre-treatment resting NRS for pain and fatigue
 - Pre-treatment Sit and Stand with NRS for pain and fatigue
- TENS applied for 1st full treatment X 30 minutes
 - Post-treatment resting NRS for pain and fatigue
 - Post-treatment Sit and Stand with NRS for pain and fatigue
- REDCap™ email sent to study staff when TENS instruction visit complete

6.2.6 90 Day Research Homework (Home +/- 5 days)

- REDCap™ sends participant reminder email to complete Day 90 Research Homework
- Log into REDCap™ to complete assessments:
 - Adverse Events
 - Pre-treatment resting NRS for pain and fatigue

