6.2.14 Questionnaires

The following questionnaires will be self-administered by participants:

- **Resting NRS for pain and fatigue**-11-point scale
- **Sit and Stand Test** – quantifies movement-evoked pain and fatigue.
- **2016 FM Criteria**- diagnostic criteria for fibromyalgia.
- **PSFS (Patient Specific Functional Scale)** – quantifies activity limitation and measures functional outcomes
- **FIQR (Fibromyalgia Impact Questionnaire Revised)**- 21 items used to evaluate function, overall impact, and symptoms in patients with fibromyalgia.
- **MAF (Multidimensional Assessment of Fatigue)**-16 items measuring fatigue according to four dimensions: degree and severity, distress that it causes, timing of fatigue, and impact on various activities of daily living.
- **BPI (Brief Pain Inventory)**- 11 items measuring pain severity and interference with daily activities.
- **PROMIS-Physical function** – assesses information about physical activities.
- **PROMIS-Sleep+Sleep duration**- 8 items + sleep duration assesses sleep quality and quantity
- **PCS (Pain Catastrophizing Scale)**- 13 items measuring pain magnification, rumination, and helplessness.
- **PHQ-8 (Personal Health Questionnaire Depression Scale)**- 8 items measuring depressive disorders.
- **GAD-7 (Generalized Anxiety Disorder)**- 7 items measuring severity of various signs of generalized anxiety disorder.
- **RAPA (Rapid Assessment of Physical Activity)**- 9 items evaluating current level of physical activity.
- **TAPS (Tobacco, Alcohol, Prescription Medication, and other Substance use)**- 4 item screening tool for substance abuse.

- **PGIC (Patient Global Impression of Change)**- one item evaluating all aspects of patients' health and assesses if there has been an improvement or decline in clinical status.

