## 1. STUDY DESIGN

### 1.1 Design

This study is a cluster-randomized pragmatic trial conducted where the initial proposed sample size was 600 across 24 physical therapy clinics. The original sample size was reduced from 600 based on a planned interim sample size recalculation following enrollment of the first ~200 participants and based on the planned interim assessment of intra-class correlation coefficient (ICC). A stratified randomization of practice sites will be employed based on healthcare system and size of the practice site (clinics) so that half of the clinics will provide transcutaneous electrical nerve stimulation (TENS) in addition to physical therapy (PT) (TENS+PT) for each enrolled participant and the other half of the clinics will provide standard of care routine individualized PT treatment (PT only). To avoid potential exposure to TENS in the clinics randomized to PT only, the clinics will be specifically instructed not to prescribe TENS to their fibromyalgia (FM) patients. Likewise, study participants in the PT only site that may be exposed to TENS through other means (relatives, friends) will also be instructed not to use TENS to prevent cross-ins. Furthermore, participants randomized to the PT only group will receive TENS unit after the primary outcome data is collected at day 60 which may also prevent cross-ins and provide equipoise. Primary analyses will be based on modified intention-to-treat which includes all participants with baseline (day 1) pre-TENS home activities.

Participants will be followed for 180 days with data collection from home at 1, 30, 60, 90, and 180 days following enrollment. Participants in the PT only group will also complete a brief assessment at day 65. The primary outcome variable will be assessed at day 60, which would be approximately at the completion of prescribed PT. Data collected at PT visits will include the types of treatments (CPT codes) and, at the clinic's usual intervals, visit type (in-person vs telemedicine), and the Patient-Specific Functional Scale (PSFS). All patient reported measures will be obtained at home via computer, tablet, or phone.

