## 3. SECONDARY ENDPOINTS

*The secondary objectives of the study are to:*

- Determine if addition of TENS to routine physical therapy improves disease activity and symptoms, increases adherence to physical therapy, increases the likelihood of meeting patient specific functional goals, and reduces medication use.*

Change in the resting pain score from baseline (pre-TENS) to 60 days (post-TENS session) will be used as a secondary outcome variable. The severity of pain will be measured on a 0 to 10 scale at each time where 0 is no-pain and 10 is worst pain imaginable. Other secondary outcomes include change in the following domains:

- o Pain interference (BPI)
- o FM disease activity (FIQR)
- o Resting fatigue (NRS)
- o Movement-evoked fatigue (MEF)
- o Multidimensional assessment of fatigue (MAF)
- o Rapid assessment of physical activity (RAPA)
- o Patient global impression of change (PGIC)

An exploratory outcome for patient-specific function using the patient-specific functional scale (PSFS) will be evaluated. Additional HEAL-specified measures and medications are located in the visit schedule. A brief description of the domains above can be found in section 1.2.

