## 7.2 Analysis

To assess the effectiveness of TENS+PT compared to PT alone, we will compare the change in movement-evoked pain during 5TSTS from pre-TENS baseline to post-TENS at day 60. The null hypothesis can be evaluated based on an assessment of parameter estimates from a linear mixed effects model (LMM: Laird & Ware, 1982). This will be tested using LMM analysis with treatment group and movement-evoked pain level at baseline as fixed effects. Randomization will be stratified by the healthcare system and clinic size. The model will be adjusted for the fixed effect of clinic size. The proposed study involves multiple clinics under each healthcare system, which is a potential source of additional variation. Patients within a clinic tend to be correlated due to similarity of environment, e.g. because of getting PT treatment from the same set of physical therapists (Localio et al, 2001). Therefore, a random effect will be included for treatment nested within clinic, and within healthcare system.

For this analysis, the LMM can be written in the following manner:

$$Y_{ijk} = \beta_0 + \beta_1 X_{1i(jk)} + \beta_2 X_{2i(jk)} + \beta_3 T_{ijk} + a_{i(j)} + \epsilon_{ijk}$$

where:

- $Y_{ijk}$  is the change in movement evoked pain level from baseline to day 60 for the  $k^{\text{th}}$  participant in  $i^{\text{th}}$  healthcare system and  $j^{\text{th}}$  clinic.
- $\beta_0$  is the common intercept.
- $X_{1i(jk)}$  is the movement evoked pain level at baseline for the  $k^{\text{th}}$  participant .
- $X_{2i(jk)}$  if the participant was in the large clinical size strata at baseline, 0 otherwise.
- $T_{ijk} = 1$  if  $k^{\text{th}}$  participant in  $i^{\text{th}}$  healthcare system and  $j^{\text{th}}$  clinic is in the TENS+PT treatment group; = 0 otherwise.
- $a_{i(j)}$  is the random clinic effect within the  $i^{\text{th}}$  healthcare system
- $\epsilon_{ijk}$  is a random error term for the  $k^{\text{th}}$  participant in  $i^{\text{th}}$  healthcare system and  $j^{\text{th}}$  clinic.

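### Baseline BPI, FIQR, MAF and RAPA are answered during the first TENS session in the TENS arm only, yet the SAP uses them as ordinary baselines and covariates

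*Protocol*

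**What the plan says.** Protocol 6.2.2 fixes the Day 1 order. Resting ratings and the Sit and Stand ratings come first. Then comes "TENS applied (or not) for at least 30 min while completing the assessments below on tablet", with PT-only participants going straight to the forms, and post-treatment ratings come last. The Schedule of Activities (Protocol 6.1) agrees: its last test is the "Sit and Stand Test with NRS pain and fatigue post TENS or no TENS treatment after 30 min of answering questionnaires". Of the 14 forms listed, FIQR, MAF and BPI are fourth to sixth and RAPA is twelfth. Day 60 (Protocol 6.2.5) also places the forms after TENS is applied in the TENS arm.

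A pre-TENS baseline is defined explicitly for movement-evoked pain (SAP 2) and resting pain (SAP 3). For the rest, SAP 3 says only "Other secondary outcomes include change in the following domains". SAP 8 sends all secondary outcomes to the methods of SAP 7, where "we will compare the change in movement-evoked pain during 5TSTS from pre-TENS baseline to post-TENS at day 60" and the baseline level is a fixed effect. SAP 1.1 states that the modified ITT set "includes all participants with baseline (day 1) pre-TENS home activities".

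Protocol 9.4 allows variables that differ significantly between arms at baseline to become covariates. SAP 5 lists FIQR among the tabulated baseline characteristics. SAP 7.4 does not name FIQR as a potential covariate.

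**The concern.** A baseline covariate should not be open to influence by the treatment. Here one arm supplies it with the device running and the other without.

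The reason to expect some influence is the sponsor's own. Protocol 2.2 reports that in the earlier trial active TENS "reduced pain and fatigue during movement and at rest acutely (during the first application". Parts of these instruments ask about the same things: FIQR is described as "21 items used to evaluate function, overall impact, and symptoms in patients with fibromyalgia", BPI covers pain severity, and MAF covers fatigue severity. The NRS outcomes are rated before the device is switched on; these forms are not.

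At stake is the meaning of three or four secondary results. A reader of the SAP would take a reported change in BPI, FIQR or MAF as change from an untreated state. There is also a smaller route. A Day 1 score shifted by TENS could differ between arms, pass the baseline-difference test in Protocol 9.4, and enter an adjusted model for any outcome, including the primary.

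**Working it through.** The plan gives no figure on this point, so there is none to reproduce.

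**Which outcomes.** There are eight secondary outcomes: resting pain plus the seven domains in SAP 3.

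| Outcome | Day 1 value | Affected? |
|---|---|---|
| Resting pain, resting fatigue, movement-evoked fatigue | rated before TENS | no |
| PGIC | not collected at Day 1 | no |
| BPI, FIQR, MAF | during the TENS session | plausibly |
| RAPA | during the TENS session | unlikely (activity level) |

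**Inputs.** From SAP 9: 450 × (1 − 0.24) = 342 participants completing Day 60, 13 clinics per group (26 in all), cluster-size CV 0.6, ICC 0.05. The documents give nothing on session shifts or baseline slopes for these forms, so these are assumptions: d1 = 0 to 0.3 SD, b = 0.5 to 0.7.

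**Formula.** Count improvement as positive, in SD of the questionnaire score. Let C be the TENS effect at Day 60 with no session running, d1 and d60 the session shifts at Day 1 and Day 60, and b the slope of the Day 60 score on baseline. Assume the arms were comparable before TENS. Using change as the response with baseline as covariate gives the same treatment coefficient as modelling the Day 60 score:

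- Arm difference at Day 60: C + d60
- Arm difference in the recorded baseline: d1
- Planned estimate: C + d60 − b × d1
- Effect from a pre-TENS baseline, session running at Day 60: C + d60
- Shortfall: b × d1

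**Shortfall.** 0.6 × 0.1 = 0.06 SD; 0.6 × 0.2 = 0.12 SD; at the top of the assumed range 0.7 × 0.3 = 0.21 SD; with d1 = 0 it is 0.

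**Does the matching Day 60 order cancel it?** Only in part. If d60 = d1 = d, the estimate is C + (1 − b) × d, which lies between the no-session effect C and the with-session effect C + d. If the first-session shift is the larger, the estimate can fall below both. With C = 0.30, b = 0.6, d1 = 0.2 and d60 = 0.05 it is 0.30 + 0.05 − 0.12 = 0.23, against 0.30 and 0.35 (simulated: 0.228). The shortfall b × d1 does not depend on d60.

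**Simulation check.** 3,000 runs with the SAP 9 inputs above, C = 0.30, b = 0.6, d60 = d1, and an assumed correlation of 0.4 between the pre-TENS NRS ratings and the Day 60 score. The last two columns replace the Day 1 questionnaire score with the pre-TENS NRS ratings.

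| d1 | Planned model | True pre-TENS baseline | NRS covariates | NRS minus planned |
|---|---|---|---|---|
| 0 | 0.300 | 0.300 | 0.302 | 0.002 |
| 0.1 | 0.340 | 0.400 | 0.399 | 0.059 |
| 0.2 | 0.380 | 0.500 | 0.500 | 0.120 |
| 0.3 | 0.415 | 0.595 | 0.595 | 0.181 |

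The last column tracks b × d1. The NRS-covariate model had a standard error 4% to 16% larger over b = 0.5 to 0.7 and correlations of 0.3 to 0.5.

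**What that comparison can show in one trial.** The difference between the two estimates has an SD of about 0.05, or 0.06 to 0.07 if the baseline score itself clusters by clinic (assumed ICC 0.05 to 0.10). At d1 = 0.1 the expected 0.06 is 0.06/0.07 = 0.9 to 0.06/0.05 = 1.2 of those SDs. At d1 = 0.2 it is 0.12/0.07 = 1.7 to 0.12/0.05 = 2.4. The comparison is also not specific. With d1 = 0 and a true 0.1 SD questionnaire imbalance not reflected in the NRS ratings, the difference was again 0.059. In that case the planned model was right (0.299 against a true 0.300) and the NRS model was not (0.357).

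**The case against.** The strongest reply is that no effect on these forms is shown. Protocol 2.2 reports acute change in pain and fatigue at rest and in movement, not in any questionnaire score. The documents give no recall periods, and much of the content concerns interference, impact or usual activity. In listed order FIQR, MAF and BPI also come well before a full 30 minutes of stimulation. This stands: d1 may be near zero, and every magnitude above is an assumption.

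Second, the order is stated openly and repeated at Day 60, so on-session is compared with on-session, and no pre-TENS baseline is explicitly promised for these domains. That is a fair description of the design. But the cancellation is partial, the model borrowed from SAP 7.2 is written for a pre-TENS baseline, and SAP 1.1 applies that label to the Day 1 activities as a whole. That these scores serve as covariates is itself an inference from SAP 8 pointing to SAP 7, though the natural one.

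Third, the sensitivity analysis cannot tell a session shift from a recruitment imbalance. SAP 6.1.1 says consent automatically places a participant in the clinic's arm, so such imbalance is possible. This stands and limits what may be claimed for the analysis.

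Fourth, the covariate-selection route is permissive, not planned: Protocol 9.4 only allows it and SAP 7.4 does not name FIQR. That also stands, but it makes closing the route easy.

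**Conclusion.** The point holds and is minor. For BPI, FIQR and MAF, and formally RAPA, the only baseline may be treatment-affected in one arm. The planned estimate then falls short of the effect from a pre-TENS baseline by b × d1: 0.06 SD at d1 = 0.1 and 0.12 SD at d1 = 0.2 with b = 0.6, and nothing if d1 = 0. This rests on assumed values of b and d1, on TENS improving scores during the session, and on arms comparable before TENS.

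Three stronger readings are not supported:

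- A reader might infer that the trial's main result is compromised. It is not: the primary and all NRS outcomes have baselines taken before the device is applied.
- A reader might infer a quantified loss of power for the secondary outcomes. The documents give no design effect or power for them, so borrowing the primary's standardised difference would be invention.
- A reader might infer that the estimate always lies between the with-session and no-session effects, or that the NRS-based analysis measures the bias. The first needs similar shifts at Day 1 and Day 60. The second needs no recruitment imbalance.

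**What to change.** 1. **Covariate rule.** State that Day 1 questionnaire scores collected during the TENS session are not eligible as covariates under the baseline-difference tests of Protocol 9.4, in the primary or any other outcome model.
2. **Sensitivity analysis.** Keep the planned model as the main secondary analysis. Add to SAP 8 one analysis of the Day 60 BPI, FIQR and MAF scores (the Day 60 score as response, not change), with the Day 1 questionnaire score replaced by the pre-TENS Day 1 NRS pain and fatigue ratings. State its limits alongside:
   - it targets the effect with a session running at Day 60;
   - its standard error is about 4% to 16% larger;
   - its difference from the planned estimate has an SD of about 0.05 to 0.07 SD, so only moderate shifts would show;
   - a difference may also reflect recruitment imbalance, because consent follows clinic allocation.
3. **Label.** Do not describe these baselines as pre-TENS. Footnote the baseline table to say that the TENS arm completed the forms during its first session.

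The cost is a few sentences of SAP text and three extra model fits on data already collected. Conduct does not change.

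Moving these forms ahead of TENS for later participants is a trade-off I would not recommend. It mixes two baseline definitions and adds time to homework whose non-completion means withdrawal (Protocol 4.4). With equal shifts, it also raises the excess over the no-session effect from (1 − b) × d to d, for example from 0.04 to 0.10 SD at d = 0.1 and b = 0.6.
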